
The proposed work will test key predictions of the FMDM account of CM with implications for (1) improved treatment effectiveness and (2) targeted treatment delivery. Individuals with CUD (n=140) will be recruited upon engagement with outpatient substance use services and assigned to 12 weeks of TangiblePBCM (n=70) or VoucherPBCM (n=70). Participants in all conditions will complete EEG and cognitive-behavioral assessments of core FMDM constructs (i.e., goal-informed cognitive control processes, executive working memory, episodic future thinking, and reward anticipation) before and after the 12 week treatment interval. Self-report measures of other clinically-relevant indicators (e.g., addiction propensity and severity, motivation, self-efficacy) will also be evaluated and outcomes (treatment engagement, subjective and objective measures of substance use) will additionally be

followed throughout the 12 week treatment interval and for 6 months post-treatment in both CM groups. Aims and hypotheses are as follows:

Specific Aim 1: Evaluate the utility of EEG and cognitive-behavioral measures of FMDM as predictors of differential treatment outcomes in TangiblePBCM versus VoucherPBCM.

Hypothesis 1a. FMDM-related measures will predict differential outcomes in TangiblePBCM relative to VoucherPBCM, with more FMDM-impaired individuals demonstrating improved treatment response in the former relative to the latter.

Hypothesis 1b. Inclusion of predictors from the FMDM account will significantly improve performance of predictive models forecasting short- and long-term outcomes in CM and inclusion of these predictors will be robust to model-based constraints favoring variables with lower measurement costs.

Specific Aim 2: Evaluate treatment-related change in EEG and cognitive-behavioral correlates of FMDM-related cognitive functioning during CM.

Hypothesis 2a. Individuals who reliably engage in TangiblePBCM and VoucherPBCM will demonstrate greater treatment-related change in functional connectivity networks underlying goal-informed cognitive control processes, as well as behavioral measures of working memory and future-oriented decision-making, relative to individuals who demonstrate poor PBCM adherence.

Exploratory Sub-Aim. Longitudinal change in FMDM-related measures will be investigated in relation to patterns of abstinence during PBCM and will reflect distinct treatment response trajectories.

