Urine and/or oral saliva specimens will be collected/tested at baseline using commercially-available drug test kits and specimen containers. We will also collect and test urine and/or oral saliva at the time of the follow-up EEG assessment. In addition, urine specimens may also be collected and tested using commercially-available drug test kits at check-in appointments if the participant is not actively involved in CM and/or has missed recent CM visits. However, it is noted that collection of such supplemental urine specimens at check-in timepoints would not apply if (1) lab-based urinalysis for substance use has recently been completed for clinical or research purposes, (2) the participant refuses, or (3) the participant is not available or able to provide a specimen. All urine and oral saliva specimens collected for testing with commercially-available drug test kits in the context of these described research activities will be marked with indirect identifiers only and will be disposed of immediately after testing.

Samples Collected in the Context of Treatment (CM; *Direct Identifiers*):

During the 12 week treatment interval, patients will be subject to routine urinalysis (twice weekly). Urine specimens will be collected (and may be witnessed, if necessary) by nursing staff at the Center for Treatment of Addictive Disorders (CTAD) or research staff at the Research Office Building and tested for cocaine (and possibly other substances) by the CM therapist using a point-of-care diptest in order to provide the patient with immediate results for the purpose of determining CM prize draws. Confirmatory urinalysis will subsequently be conducted to verify point-of-care results. Urine specimens will therefore be forwarded to VAPHS laboratory staff for processing. For this reason, urine specimens collected in the routine clinical course of CM will be marked with direct identifiers prior to submission to the lab. However, it is noted that all urine collection/testing procedures to be conducted within the context of CM parallel those already used in routine clinical (i.e., non-research) administration of CM and other substance use treatment programming at VAPHS. It is additionally noted that participants may always decline to provide observed urines for lab-based processing and may alternately elect to provide urine specimens (not marked with direct identifiers) for kit-based testing by research personnel, as described above.

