- Breathalyzer and Oral Saliva Drug Testing: Participants will be required to pass breathalyzer (BAC = 0.000%), as well as urine and/or oral saliva drug screens (negative for all common illicit substances, excluding marijuana) in order to participate in baseline testing. Such testing is necessary to establish that participants are not acutely intoxicated at the time of EEG and cognitive-behavioral assessments, which may compromise the validity and reliability of these measures. We will offer oral saliva testing as an option because this method has an earlier and more proximal detection window than urine-based testing (sensitive to use immediately prior to testing and during the preceding 72 hours). Consequently, it will be possible to include CUD participants with relatively short durations of cocaine abstinence prior to baseline testing. Participants will be informed of drug and alcohol testing procedures at the screening visit and asked to abstain from drug use for 72 hours prior to testing. While this requirement will necessarily exclude individuals who are unable to abstain for 72 hours, such individuals would generally not be recommended for CM programming (VA CM implementation consultants suggest 3-4 days of demonstrated abstinence prior to initiating a CM referral). Consequently, this requirement should not prevent us from achieving a representative sample of cocaine users for whom CM is indicated. Due to

the requirement that participants pass initial drug-alcohol screening, individuals with anticipated or observed difficulty achieving initial abstinence may elect to schedule one or more optional pre-CM testing sessions with study personnel in preparation for the Baseline session.

▪ **Timeline Follow-Back (TLFB) Procedure:** During the timeline follow-back, participants will be asked to describe drug and alcohol use during the past month, including type, frequency, and quantity. Typical patterns of pre-treatment drug and alcohol use may also be evaluated if a recent change in use has preceded the testing session (for example, patient completed residential treatment during the past month).

EEG Procedure: Participants will complete two computerized behavioral tasks while EEG is recorded from the surface of the scalp using a commercially-available EEG recording system. A baseline (resting) acquisition may also precede task-related data acquisition, as is typical for EEG recording procedures.

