Follow-up Visit: A subset of procedures from the Screening/Baseline Assessment will be repeated at the conclusion of the 12 week treatment interval for all participants. Procedures will generally involve repetition of the EEG procedure, re-administration of cognitive/cognitive-behavioral testing, and re-administration of one or more self-report questionnaire measures. The timeline follow-back procedure will generally also be completed again at the time of the follow-up visit and specific items from the Addiction Severity Index Lite may also be re-administered. To optimize test-retest reliability of the Personalized Delay Discounting task (if applicable), we will attempt to identify a new set of personally-relevant future event tags with similar valence, salience, and arousal to those utilized at Baseline Assessment through repetition of the Positive-Neutral Future Events interview at the time of the Follow-up Visit. A-B variants of cognitive/cognitive-behavioral tests may also be employed as needed. It is noted that, in some cases, the follow-up visit may occur earlier or later than 12 weeks following treatment initiation. Some flexibility in the timing of the follow-up session may be necessary in order to

maximize our opportunities to collect post-treatment data on as many participants as possible. It is, for example, possible that a participant might conclude treatment earlier than 12 weeks due to returning to work or moving out of the area. In such cases, we would invite the participant to complete the follow-up session early. Similarly, delays in scheduling of the follow-up session may also occur for a variety of reasons. Provided that the participant is still willing to complete the follow-up session, this session may therefore also be scheduled to occur more than 12 weeks from the start of treatment. For healthy controls, a follow-up visit will also be conducted after the initial session, at a delay similar to that achieved within the patient sample. This session may include repetition of other measures conducted at baseline, which can include the repetition of the EEG procedure, cognitive-behavioral testing, and/or self-report questionnaires.

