To address limitations related to the ratio of observations to predictors in the context of our reduced sample size, we revised our predictive analytic approach (Specific Aim 1) to prioritize model stability and interpretability, while framing results as more preliminary in nature. With respect to Aim 1, a revised sample size of ~50 participants was identified as sufficient to support investigation of up to five candidate predictors: e.g., two EEG-derived metrics, one clinical measure, one neurocognitive measure, and treatment condition. Recent simulation-based work (Austin & Steyerberg, 2015) further suggests that as few as two participants per predictor may be adequate, supporting investigation of the original candidate set even within the reduced sample. Two consulting biostatisticians endorsed this revised approach and further recommended modeling repeated binary outcomes over the course of CM treatment to improve power. In line with this recommendation, we modeled 24 repeated binary outcomes per participant, yielding up to $24 \times n$ observations across n participants. However, recognizing that the effective number of independent events remains tied to the number of participants rather than the number of observations, we adopted a two-stage variable selection process to reduce the risk of overfitting. In the first stage, we screened predictors using single-predictor longitudinal logistic regression models, identifying those with theoretically plausible associations with the outcome. This process narrowed our total number of candidate predictors. In the second stage, we applied stepwise forward selection guided by the Akaike Information Criterion (AIC) to construct a parsimonious, interpretable multivariate model. To further assess model robustness and generalizability, we evaluated predictive performance using leave-one-out cross-validation (LOOCV).

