Implications of our reduced sample size were also considered for Specific Aim 2, which involves longitudinal analysis of change in key neurocognitive metrics with adherence and abstinence as potential covariates. Based on guidance from statistical consultants, a sensitivity analysis indicated that a total sample size of 36 participants with both pre- and post-treatment data would provide adequate power to detect small to medium effect sizes ($f = 0.17\text{--}0.30$). This revised projection reflects the practical constraints of the available sample while maintaining sufficient power for detecting meaningful change over time in the context of repeated measures analysis. As an alternative analytic strategy, a median split approach to adherence and abstinence may be considered if data suggest that dichotomization would enhance interpretability or improve model stability in the context of limited sample size. While treating these variables as continuous covariates is generally preferred due to increased power and retention of variance, a binary approach may be appropriate in cases of non-linear relationships, bimodal distributions, or when simplifying the model structure offers clear interpretive advantages.

Specific Aim 1. Evaluate the utility of EEG and cognitive-behavioral measures of FMDM as predictors of differential treatment outcomes in TangiblePBCM versus VoucherPBCM. A significant interaction between CM treatment condition (i.e., TangiblePBCM versus VoucherPBCM) and neurocognitive indices

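### Aim 2 excludes everyone lost to follow-up although a mixed model could keep them; secondarily, the drug screen at the follow-up EEG has no stated role in the analysis

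*Combined protocol and SAP*

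**What the plan says.** Hypothesis 2a (section 2, study objectives) predicts greater change in reliable engagers "relative to individuals who demonstrate poor PBCM adherence". Section 4.1, Specific Aim 2, tests it by repeated-measures ANCOVA of baseline against follow-up for three measures: theta synchrony, Brown-Peterson score and delta ln(k). The revised sample-size text describes Aim 2 as "longitudinal analysis of change in key neurocognitive metrics with adherence and abstinence as potential covariates". It adds: "While treating these variables as continuous covariates is generally preferred due to increased power and retention of variance". A median split is the fallback.

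**Loss to follow-up.** The Aim 2 missing-data paragraph excludes those lost to follow-up, on the ground that the analysis needs follow-up measures. Imputation is mentioned only for unexpected circumstances, and no model is given.

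**Sample sizes.** For Aim 1, "a revised sample size of ~50 participants was identified as sufficient" for up to five candidate predictors. For Aim 2, a sensitivity analysis takes 36 participants with both assessments and quotes f = 0.17 to 0.30. Both are planning sizes.

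**Drug screening.** Under Baseline Assessment (section 4), breathalyzer and drug screens must be passed "in order to participate in baseline testing. Such testing is necessary to establish that participants are not acutely intoxicated at the time of EEG" and cognitive assessments. Section 3.5 says: "We will also collect and test urine and/or oral saliva at the time of the follow-up EEG assessment". The Follow-up Visit text says "A subset of procedures from the Screening/Baseline Assessment will be repeated at the conclusion of the 12 week treatment interval". None of the visible text says what follows from a positive follow-up result, and Aim 2 gives the result no role. Percent days of use, percent sessions attended and PBCM condition are optional covariates. The Study Procedures Table and session forms are listed but not reproduced, so this describes the visible text only.

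**The concern.** Adherence is not randomised, so Hypothesis 2a rests on an observational contrast within a small sample.

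Participants who return for the second EEG may differ from those who do not. If return depends on baseline score, regression to the mean shifts the average change among completers. If that dependence, or the return rate, differs by adherence, the shift does not cancel in the adherence-by-time contrast. Discarding baseline-only participants removes the data that could correct it.

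The screen raises a second, smaller issue. Drug status is held negative at baseline by design, so screen differences can arise only at follow-up and enter the change score directly. If poor adherers are more often positive, and recent use affects these measures, part of a smaller change could reflect recent use rather than less neuroadaptation.

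**Working it through.** **1. The plan's own figures.** For two groups and m = 2 time points, the noncentrality is lambda = N f² m / (1 − rho), with 1 and N − 2 df, alpha 0.05 and 80% power. The plan gives no pre-post correlation rho.
- At rho 0.5, detectable f is 0.119 for N = 140 (plan: 0.12) and about 0.13 for N = 119 (plan: 0.13).
- At N = 36, f is 0.300, 0.240 and 0.170 at rho 0.22, 0.50 and 0.75. This matches the plan's 0.17 to 0.30, although the plan does not say what varies.
- At rho 0.5 the SD of change is sqrt(2(1 − 0.5)) = 1. With 18 per group, lambda = 144 f² = 9 D², so D = 4f, a detectable difference of 0.961 SD.

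**2. Loss to follow-up.** With no true effect, expected change given a standardised baseline score y is −(1 − rho) y. The completers-only bias in the contrast (adherers minus poor adherers) is therefore (1 − rho)(m_N − m_A). Here m_N and m_A are the mean baseline scores of those followed among poor adherers and adherers.

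Assumed scenario, not document counts: 50 at baseline and 36 followed on average (72%), with follow-up of 80–84% in adherers and 60–64% in poor adherers, and rho 0.5. Log-odds of being followed are per SD.

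| Follow-up depends on | Completers-only bias (SD) | False positives at nominal 5% | Likelihood-model bias (SD) |
|---|---|---|---|
| adherence only | 0.00 | 5% | 0.00 |
| also baseline score, 0.6 in both groups | +0.04 to +0.07 | 5–6% | 0.00 |
| also baseline score, 0.2 in adherers, 0.6 in poor adherers | +0.08 to +0.10 | 6% | 0.00 |
| also baseline score, 0.2 and 1.0 | +0.13 to +0.15 | 6–7% | 0.00 |
| unobserved change instead of baseline, 0.2 and 1.0 | −0.26 to −0.30 | 12–14% | −0.20 to −0.23 |

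The largest baseline-related bias, 0.15 = 0.5 × 0.30, means that followed poor adherers start 0.30 SD above followed adherers. Against 0.961 SD, the range is 0.04/0.961 = 4% to 0.15/0.961 = 16%. A positive sign favours Hypothesis 2a. By symmetry it reverses if low scorers are the ones more likely to return. The likelihood model removes this bias because it evaluates follow-up at the baseline mean of everyone enrolled in each group.

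**3. The follow-up screen.** Section 4 describes saliva testing as "sensitive to use immediately prior to testing and during the preceding 72 hours". That is 3 of 84 treatment days, or 3.6%, so a covariate averaged over the period can miss it. If recent use lowers the follow-up score, bias = effect × gap in positive rates. All inputs here are assumed (N = 36, rho 0.5):
- 0.3 SD × 20 points = 0.06 SD; false positives about 5%, essentially nominal.
- 0.5 SD × 40 points = 0.20 SD, which is 21% of 0.961; about 9%.
- 0.8 SD × 60 points = 0.48 SD; about 27%.

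Adding a period-use covariate in the middle case leaves 0.05 to 0.19 SD of the 0.20 SD, depending on how closely period use tracks the screen.

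**4. Conditioning on the screen has its own bias.** Assume no drug-state effect, no adherence effect, and 50% against 10% positive. Add an unmeasured cause correlated 0.3–0.7 with underlying use and 0.3–0.5 with change. The unadjusted contrast is then unbiased (0.00). The screen-adjusted contrast is off by −0.06 to −0.24 SD, and the screen-negative-only contrast by −0.05 to −0.21 SD. That is as large as the 0.20 SD the check is meant to detect.

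**The case against.** **On loss to follow-up.** The biases are modest, and zero if loss depends on adherence alone. Poor adherence is not the same as loss: participants may stay in the research after stopping contingency management (section 7), and follow-up timing is flexible (section 4). Section 4.1 allows imputation and alternative methods for the reduced sample. The mixed model only partly helps if loss depends on unobserved change. All of this stands and limits the size of the point. It does not rescue the stated reason for exclusion, and neither allowance specifies a method for dropout.

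A reader might infer from the figures 50 and 36 that 28% were lost. The documents do not support that: one is a size judged sufficient for Aim 1, the other a sensitivity-analysis size for Aim 2.

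**On the screen.** A reader might infer that Aim 2 ignores drug use, or that less neuroadaptation cannot be told apart from recent use. Neither follows. Percent days of use and abstinence are optional covariates, timeline follow-back is generally repeated at the follow-up visit, and urine is tested twice weekly during treatment. These could identify much of the recent use, although Aim 2 does not prespecify using them that way. Nor do the baseline and follow-up texts contradict each other; the follow-up text is silent on what a positive result means.

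The plan says only that intoxication may compromise these measures, so the direction assumed in step 3 is not a document fact. Section 4.1 also permits further unlisted analyses, so later use of the screen is unplanned rather than ruled out.

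**Conclusion.** The main point holds: excluding those lost to follow-up is a choice, not a necessity. It biases the adherence-by-time contrast when loss depends on baseline score, most clearly when it does so differently by adherence. The size is about 0.04 to 0.15 SD under the assumed dropout odds, rho 0.5 and an assumed 36 of 50 followed. A likelihood-based model brings this to about zero, with slightly better precision, but does not resolve loss related to unobserved change.

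The secondary point holds in a limited form. The follow-up screen has no stated analytic role, and recent use may contribute to a smaller change in poor adherers. Its size and direction are unknown, and at the low end of the assumed range it has almost no effect. It would be tempting to say that adjusting for the screen corrects Hypothesis 2a. It does not: a positive result shows recent use rather than intoxication, it arises after treatment begins, and it may itself follow from poor adherence.

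**What to change.** 1. Replace the completers-only ANCOVA with a likelihood-based linear mixed model (adherence × time) that keeps everyone with a baseline. Attendance comes from session logs and chart review, so adherence does not depend on the follow-up visit. Compare baseline scores and adherence between those with and without follow-up. State that the model handles loss related to adherence or baseline score, not loss related to unobserved change.
2. Keep the Hypothesis 2a model unadjusted for the screen as primary. Report follow-up screen status by adherence and specimen type. Add one sensitivity analysis, either restricted to screen-negative follow-up visits (mirroring the baseline condition) or adjusted for the screen, with adherence in the same form as in the primary model. Label it post hoc if Aim 2 has already been run. State the limits of the screen given in the verdict, and that conditioning on it can introduce bias if use and change share an unmeasured cause. It tests robustness only.
3. Reconcile section 3.5 with the Baseline Assessment and Follow-up Visit text in section 4 on how the follow-up screen result is handled. No rule is proposed here.

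**Cost.** SAP wording and small analyses on data the plan already collects, provided follow-up specimens were obtained. Precision falls only in the sensitivity analysis. In the assumed case of 50% against 10% positive, detectable f rises from 0.240 to 0.267 with adjustment, or to 0.304 with restriction, which keeps 36 × 0.70 = about 25. Over the wider assumed range it is 0.246–0.318 adjusted and 0.256–0.440 restricted.

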of FMDM function (i.e., EEG and cognitive-behavioral measures) is hypothesized. Specifically, individuals demonstrating greater FMDM impairment (poorer working memory function, less reduction in delay discounting with inclusion of future event tags, and reduced EEG/ERP signaling to abstract future reward and control demands) will achieve better outcomes in Tangible PBCM, relative to VoucherPBCM (Hypothesis 1a). In models including PBCM treatment condition as a factor, inclusion of EEG and cognitive-behavioral predictors is expected to significantly reduce prediction error with respect to both PBCM treatment response and long-term outcomes. Differential alpha suppression in response to tangible prize versus voucher prize rewards, in particular, will assay engagement by different types of future reward utilized in TangiblePBCM and VoucherPBCM. Consequently, differential alpha suppression is expected to be an especially robust predictor of outcomes in existing PBCM variants. It is further hypothesized that this candidate biomarker will be selected for inclusion in a readily translatable predictive model – even when incorporating resource constraints that penalize predictors derived from more costly procedures (e.g., EEG incurring a greater cost-based penalty than self-report measures; Hypothesis 1b).

The proposed design affords measurement of all candidate predictors prior to initiation of PBCM, as well as monitoring of both CM treatment response and long-term outcomes for all CM recipients. Predictive models of CM treatment response and long-term outcomes will be developed separately, with the caveat that our revised final sample size may not support the latter. Candidate predictors will include pretreatment FMDM-related EEG (concrete versus abstract alpha suppression, ERN amplitude, parametric N2 amplitude effect) and cognitive-behavioral measures (Brown-Peterson score, $\Delta \ln(k)$), as well as clinical indicators (e.g., craving severity, past month cocaine use, number of previous treatment episodes) and self-report scores. In order to examine the interaction between candidate predictors and CM reward parameters, PBCM condition (TangiblePBCM versus VoucherPBCM) will also be considered as an explanatory variable in predictive models.

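### LOOCV follows outcome-based predictor selection, and the plan does not say that selection is repeated in each fold; run as described, the generalizability estimate is optimistic

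*Combined protocol and SAP*

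**What the plan says.** The revised Aim 1 approach is set out in Section 4.1 under Power Analysis and Sample Size, in the past tense and as a sequence. First: "In the first stage, we screened predictors using single-predictor longitudinal logistic regression models, identifying those with theoretically plausible associations with the outcome". Next: "In the second stage, we applied stepwise forward selection guided by the Akaike Information Criterion (AIC) to construct a parsimonious, interpretable multivariate model". Last: "To further assess model robustness and generalizability, we evaluated predictive performance using leave-one-out cross-validation (LOOCV". The Specific Aim 1 text refers back to this approach and adds the per-session outcome coding, but nothing on validation. The five-fold and out-of-bag checks described there belong to the original tree and random forest plan.

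The paragraph accepts that the participant is the independent unit, "recognizing that the effective number of independent events remains tied to the number of participants rather than the number of observations", but does not say which unit LOOCV leaves out. It names no performance metric and no screening cut-off.

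The number of candidates is not fixed. The plan says "a revised sample size of ~50 participants was identified as sufficient to support investigation of up to five candidate predictors", then cites a less demanding rule as "supporting investigation of the original candidate set even within the reduced sample". Under Specific Aim 1 the candidates are EEG and cognitive-behavioral measures, "as well as clinical indicators (e.g., craving severity, past month cocaine use, number of previous treatment episodes) and self-report scores", with no count. Results are to be framed as preliminary.

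**The concern.** Both selection stages use the outcome. If they are run once on all participants before LOOCV, the held-out participant's data have already influenced which predictors are in the model. Each fold then re-estimates coefficients for a list that was chosen to fit that participant too. The variability that selection introduces never enters the estimate.

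This matters because LOOCV is the only evidence of generalizability in the revised Aim 1 plan, and the two-stage selection is presented as protection against overfitting. A validation step that skips the selection cannot show whether that protection worked. The stage-1 rule is also a judgment of plausibility with no threshold or direction, so it cannot be repeated by fold as written.

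A secondary point: Specific Aim 1 states that "inclusion of EEG and cognitive-behavioral predictors is expected to significantly reduce prediction error with respect to both PBCM treatment response and long-term outcomes", but the revised plan describes no held-out comparison with and without those measures.

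**Working it through.** **The plan's own figure.** Section 4.1 uses 10 observations per predictor: 10 × 5 = 50, so the figure of about 50 participants for five candidates reproduces. The alternative rule of two participants per predictor would allow 50 / 2 = 25. The measures named under Specific Aim 1 give 3 EEG + 2 cognitive-behavioral + 3 example clinical indicators + condition = 9. One score for each of the 12 questionnaires listed in Section 4 would make 9 + 12 = 21. The plan states no total.

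**Check by hand.** Take k independent candidates with no effect, screened at p<α. Forward AIC admits a first predictor when its likelihood-ratio statistic exceeds 2 (p<0.157), so anything that passes p<0.10 also passes AIC. The chance that at least one noise predictor is selected is 1 − (1 − α)^k:

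- k = 5: 1 − 0.9^5 = 0.41
- k = 9: 1 − 0.9^9 = 0.61
- k = 20: 1 − 0.9^20 = 0.88
- k = 5 with a pre-specified direction for the four continuous candidates: 1 − 0.95^4 × 0.90 = 0.27

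The simulated rates at which fixed-predictor LOOCV beats an intercept-only model are 42%, 58%, 88% and 27%. That check therefore passes about as often as anything is selected at all.

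**Simulation 1: no signal, random-intercept logistic model, leave one participant out.** From the plan: 50 participants, 24 sessions, five candidates including condition. Assumed: random-intercept SD 1.5, 50% success, independent predictors, and the cut-offs shown. The entries are the share of datasets in which LOOCV log-loss beats intercept-only.

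| Scenario | Predictors fixed first | Selection in every fold |
|---|---|---|
| 5 candidates, p<0.05 | 25% | 12% |
| 5 candidates, p<0.10 | 42% | 17% |
| 5 candidates, p<0.20 | 53% | 19% |
| 5 candidates, p<0.10 plus direction | 27% | 13% |
| 5 candidates, p<0.10, condition forced in, condition-only comparator | 41% | 15% |
| 9 candidates, p<0.10 | 58% | 15% |
| 20 candidates, p<0.10 (linear approximation) | 88% | 25% |

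Monte Carlo standard error is about 1 to 2 points for five candidates. The forced-condition and 9-candidate rows use 300 datasets each and are less precise. At five candidates and p<0.10, mean cross-validated R² is +0.024 fixed against −0.046 nested, and the fixed value exceeds 0.10 in 6% of datasets. AUC is about 0.54 when a model is selected. Once a noise predictor has been selected, fixed-predictor LOOCV favours the model in 94% of datasets, against 39% nested.

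A linear approximation gave 41 to 44% against 17 to 18% for the same case. With AIC alone and no p cut-off it gave 59% against 21%, so the assumed threshold does not create the effect.

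**Simulation 2: comparison with performance in new participants.** Separate code, random-intercept SD 2.0, participant-level linear models, 200 runs per scenario, cut-offs none, 0.20 and 0.10. R² = 1 − (held-out squared error of the model) / (held-out squared error of intercept-only). No signal:

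| Candidates | R² fixed | R² nested | R² true | AUC fixed | AUC true |
|---|---|---|---|---|---|
| 5 | +0.03 | −0.04 to −0.05 | −0.05 to −0.07 | 0.57 | 0.50 |
| 10 | +0.05 to +0.06 | −0.09 to −0.15 | −0.08 to −0.14 | 0.58–0.59 | 0.50 |
| 21 | +0.10 to +0.14 | −0.15 to −0.39 | −0.16 to −0.36 | 0.61–0.63 | 0.50 |

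AUC is overstated by about 0.07, 0.08 to 0.09, and 0.11 to 0.13 respectively. With two real predictors (assumed log-odds 0.6 per SD) and five candidates, R² is +0.13 to +0.14 fixed against +0.03 to +0.04 true. The fixed estimate was optimistic on average in all 18 scenarios, and nested R² stayed within about 0.04 of the truth.

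**Does nesting discard real signal?** In Simulation 1 with one true predictor among five (assumed log-odds 0.8 per SD), nested LOOCV still beat intercept-only in 86 to 88% of datasets. R² was 0.15 to 0.16 nested against 0.19 fixed.

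**The case against.** The strongest reply is that silence is not error. One narrative paragraph need not give the computing order, no LOOCV result appears in the documents, and nesting may have been done. This stands in part: the finding is about the procedure as described, not a proven mistake in the analysis.

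The second reply concerns size. With five candidates the gain under no signal is slight, and few readers would take an AUC of 0.54 as evidence of generalizability. The two simulations differ (0.54 and 0.57), so the size depends on assumptions. Beating intercept-only is not a criterion in the plan, the p cut-offs are assumed, and the 9-, 20- and 21-candidate cases rest on counts the plan does not give. All of this is fair. It limits the magnitude but not the direction, which held in every setting tried.

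Third, a screening rule written now validates that rule, not the judgment already exercised. This also stands, and is why the timing of the rule should be disclosed and several thresholds shown.

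Fourth, the original plan was not uniformly better. Its random forest used out-of-bag error, but its Tabu-search regression step had no held-out check described. Finally, the preliminary framing tempers interpretation but does not remove bias from an estimate. Hypothesis 1a concerns a condition-by-measure interaction. That was not simulated, and nothing is claimed about it here.

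**Conclusion.** The concern holds. Followed in its stated order, the revised Aim 1 procedure gives an optimistic LOOCV estimate, and nothing elsewhere in the document changes that order. In data without signal and with five candidates, LOOCV favours the fitted model in about 42% of datasets instead of 17%, and AUC is overstated by roughly 0.04 to 0.07. The optimism is substantial if something like the full original candidate set was screened.

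The direction follows from the procedure. The sizes rest on assumed cut-offs, random-intercept SD, independent predictors and candidate counts. If LOOCV leaves out single sessions, the participant's other sessions stay in the training data and would add further optimism; this was not simulated. The change should be made before the LOOCV figure is used as evidence of generalizability. The selected model can still be presented as exploratory.

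**What to change.** 1. State the number of candidates screened, and write stage 1 as a mechanical rule: a threshold and, if used, the expected direction for each predictor. If the rule is written after the screen was run, say so and show results at two or three thresholds.
2. Leave out one participant at a time, removing all 24 sessions together, and repeat screening and forward AIC in every fold.
3. Report nested log-loss and AUC against an intercept-only model as the measure of generalizability. Log-loss is the cleaner of the two, because LOOCV pulls AUC slightly below 0.50 when there is no signal (about 0.47 nested).
4. Label any non-nested figure as conditional on selection and optimistic.
5. Secondary: if the prediction-error part of Hypothesis 1b is to be claimed, compare nested error with and without the FMDM measures, and judge the difference by permuting that block across participants.

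The cost is a rerun of existing data and code in about 50 folds, plus investigator time to turn the plausibility judgment into a rule. Reported performance will be lower. If selection was already nested by participant, a sentence saying so is enough for the main point.
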